#### **6.4 Pharmacokinetic Concentrations**

Plasma concentrations of xisomab 3G3 as determined at the collection times and per the bioanalytical method described in Section 6.1 and Section 6.2, respectively, will be used for the calculation of the plasma xisomab 3G3 PK parameters.

### **6.5 Noncompartmental Pharmacokinetic Analysis and Parameter Calculation**

#### **6.5.1 Plasma Pharmacokinetic Parameters**

The appropriate noncompartmental PK parameters will be calculated from the plasma free xisomab 3G3 concentration-time data using Phoenix® WinNonlin® Version 7.0 or higher. Actual sample times will be used in the calculations of the PK parameters. The calculation of the actual time for xisomab 3G3 will be in respect to the start of infusion time of xisomab 3G3 on Day 1. All PK parameters included in the protocol are listed in Table 6.1 below, and are defined as appropriate for study design.

**Table 6.1. Noncompartmental Pharmacokinetic Parameters to be Calculated**

Parameter Label to be Used in the Text, Tables and Figures	Definition	Method of Determination
AUC0-t	Area under the concentration-time curve from time 0 to the time of the last measurable non-zero concentration	Calculated using the Linear Trapezoidal with Linear Interpolation Method
AUC0-inf	Area under the concentration-time curve from time 0 extrapolated to infinity	$AUC0-inf = AUC0-t + (C_{last}/k_{el})$ where $C_{last}$ is the last observed/measured concentration
AUC%extrap	Percent of AUC0-inf extrapolated	$AUC\%extrap = (1 - AUC0-t/AUC0-inf) * 100$
AUMC0-inf*	Area under the moment curve from time 0 extrapolated to infinity	$AUMC0-inf = AUMC0-t + [(t_{last} \times C_{last}) / k_{el}] + [C_{last} / (k_{el})^2]$
Cmax	The maximum observed concentration	Taken directly from bioanalytical data
Tmax	The time to reach Cmax. If the maximum value occurs at more than one time point, Tmax is defined as the first time point with this value	Taken from clinical database as the difference in the start time of the infusion and the time of the blood draw which is associated with the Cmax.
Kel	Apparent first-order terminal elimination rate constant calculated from a semi-log plot of the plasma concentration versus time curve	The parameter will be calculated by linear least-squares regression analysis using the maximum number of points in the terminal log-linear phase (e.g., three or more non-zero plasma concentrations).
t 1/2	Apparent first-order terminal elimination half-life	Calculated as: $0.693 / k_{el}$
CL	The apparent total plasma clearance after IV administration	Calculated as: $Dose / (AUC0-inf)$
MRT*	Mean residence time of free drug in the systemic circulation when the drug concentrations are extrapolated to infinity	Calculated as: $(AUMC0-inf / AUC0-inf) - (T_{1/2})$ Where TI is the duration of infusion
Vss	Total apparent volume of distribution following single IV dose administration	Calculated as: $MRT \times CL$

\* AUMC0-inf and MRT values will be used for Vss calculation but will not be listed in the PK tables. Note for the programmer: Parameters which are calculated for use in the calculation of a separate parameter but that are not summarized in the PK tables (i.e., AUMC0-inf and MRT) will be included in the study data tabulation model (SDTM) PP(Pharmacokinetic Parameters) domain, but not included in the analysis data model (ADaM) ADPP (Pharmacokinetic Parameters Analysis) domain.

PK parameters will not be calculated for patients with 2 or fewer consecutive time points with detectable concentrations. Subjects for whom there are insufficient data to calculate the PK parameters will be included in the concentration tables only and excluded from the summary statistics.

For the calculation of the PK parameters, plasma concentrations below the limit of quantitation (BLQ) prior to the first quantifiable concentration will be set to 0 and plasma concentrations BLQ after the first quantifiable concentration will be treated as missing.

The Kel will be determined using linear regressions composed of least 3 data points. The Kel will not be assigned if 1) the terminal elimination phase is not apparent, 2) if Tmax is one of the 3 last data points, or 3) if the R^2 value is less than 0.75. In cases where the Kel interval is not assigned, the values of AUC0-inf, AUC%extrap, AUMC0-inf, t1/2, CL, MRT, and Vss are considered not calculable and will not be reported. Wherever the resulting t1/2 is more than half as long as the sampling interval, the Kel values and associated parameters (AUC0-inf, AUC%extrap, AUMC0-inf, t1/2, CL, MRT, and Vss) may not be presented as judged appropriate and in accordance with Celerion SOPs.

## 6.6 Data Summarization and Presentation of PK Parameters

All plasma xisomab 3G3 PK concentrations and/or PK parameters descriptive statistics will be generated using SAS® version 9.3 or higher. A concentration table will be presented for pooled placebo samples without descriptive statistics.

The plasma concentrations of xisomab 3G3 will be listed and summarized by treatment and time points for all subjects in the PK population. Plasma concentrations of xisomab 3G3 will be presented with the same level of precision as received from the bioanalytical laboratory. Summary statistics, including sample size (n), arithmetic mean (Mean), standard deviation (SD), coefficient of variation (CV%), standard error of the mean (SEM), minimum, median, and maximum will be calculated for all nominal concentration time points. Excluded subjects will be included in the concentration listings, but will be excluded from the summary statistics and noted as such in the tables. All BLQ values will be presented as “BLQ” in the concentration listings and footnoted accordingly.

Mean and individual concentration-time profiles will be presented on linear and semi-log scales. Linear mean plots will be presented with and without SD.

Plasma xisomab 3G3 PK parameters will be listed and summarized by treatment for all subjects in the PK population. Pharmacokinetic parameters will be reported to 3 significant figures for individual parameters, with the exception of  $t_{1/2}$  and  $T_{max}$ , which will be presented with 2 decimal places. Summary statistics (n, Mean, SD, CV%, SEM, minimum, median, maximum, geometric mean [Geom Mean] and geometric CV% [Geom CV%]) will be calculated for plasma xisomab 3G3 PK parameters. Excluded subjects will be listed in the PK parameter tables, but will be excluded from the summary statistics and noted as such in the tables.

The level of precision for each concentration and PK parameter statistic will be presented as follows:

- minimum/maximum: in same precision as in the bioanalytical data for concentrations and same precision for PK parameters presentation
- Mean/median/Geom Mean: in one more level of precision than minimum/maximum
- SD/SEM: in one more level of precision than Mean/median/Geom Mean
- n will be presented as an integer
- CV% and Geom CV% will be presented to the nearest tenth

## **7. PHARMACODYNAMICS**

### **7.1 Pharmacodynamic Assessment**

Pharmacodynamic (PD) assessment will include evaluation of drug potency and efficiency of HD.

#### **7.1.1 Drug potency**

Drug potency will be evaluated using the following PD markers:

- Thrombus accumulation will be evaluated by a visual inspection of the dialyzer membrane at the end of HD procedures and by a gradation using a standardized visual assessment scale;
- Total protein accumulation within the HD filter will be evaluated using appropriate methods;
- Coagulation parameter (activated partial thromboplastin time [aPTT]).

#### **7.1.2 Efficiency of HD**

Efficiency of HD will be assessed by:

- Blood BUN and potassium levels before and after dialysis;
- Length of HD – will be calculated as end time minus start time in hours and presented in individual and mean tables for each treatment;

- Total dialysate urea (measurement of BUN removed over 4 hours of dialysis) will be used to calculate;
  - Single pool Kt/V. The formula to calculate Kt/V is listed under Section 7.2.3.
  - URR measured as the difference between urea pre-dialysis and post-dialysis expressed as a percentage. The formula to calculate URR is listed under Section 7.2.3.

## 7.2 Data Summarization and Presentation of PD Parameters

### 7.2.1 aPTT

**Sample Collection:** Samples for the coagulation parameter (aPTT) will be collected at screening, pre- and post-dialysis on Days -7, -5, -3, 1, 3, 5, and 12. Additional samples for aPTT will be collected following xisomab 3G3/placebo dosing on Day 1 at predose (hour 0, at least 1 hour prior the start of HD session) and at 0.167, 0.5, 1, 2, 3, 4, 6, 8, 12, 16, 24, 48, 96, 120, 144, and 192, hours after xisomab 3G3 start of infusion.

**Baseline Calculation Method Following Day 1 Dosing:** Following xisomab 3G3 dosing on Day 1, aPTT change from baseline will be calculated by dividing postdose aPTT values from average of pre-dose baseline (the average of pre-dialysis aPTT values on Days -7, -5, -3, and 1 will be calculated as pre-dose baseline).

**Fold change in aPTT values:** The fold change in aPTT values on Days -7, -5, -3, 1 (only pre- and post-dialysis aPTT values on Day 1), 3, 5, and 12 will be calculated by dividing the post-dialysis aPTT/pre-dialysis aPTT values for each day separately.

aPTT values will be extracted from the clinical laboratory database and descriptive statistics will be generated using SAS® version 9.3 or higher. Following Day 1 xisomab 3G3 dosing, a table will be presented for the aPTT change from baseline with descriptive statistics.

aPTT values will be listed and summarized by treatment and time points in Tables and Figures for all subjects in the Safety Population (2 active dose levels and pooled placebo). aPTT values will be presented with the same level of precision as received from the clinical laboratory database. Summary statistics, including n, Mean, SD, CV%, SEM, minimum, median, and maximum will be calculated for all nominal values time points. Excluded subjects will be included in the aPPT values tables, but will be excluded from the summary statistics and noted as such in the tables.

Mean and individual aPTT values-time and change from baseline-time profiles will be presented on linear scale. Linear mean plots will be presented with and without SD.

The level of precision for the aPPT values summary statistic will be presented as follows:

- minimum/maximum: in same precision as in the clinical laboratory database
- Mean/median: in one more level of precision than minimum/maximum
- SD/SEM: in one more level of precision than Mean/median
- n will be presented as an integer
- CV% will be presented to the nearest tenth

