| | Hours → | | start | end | start | end | start |
| Safety Evaluations | | | | | | | |
| Abbreviated Physical Examination ^{e:} | | | | | | | X ^{r:} |
| Weight | | X ^{f:} | X ^{g:} | X ^{f:} | X ^{g:} | X ^{f:} | X ^{g:} |
| 12-Lead Safety ECG | | | | | | | X ^{r:} |
| Vital Signs (HR, BP, RR, and T) | | X ^{f:} | | X ^{f:} | | X ^{f:} | X ^{r:} |
| Bleeding of Access Site | | | | | | | X ^{g:} |
| Hem, Serum Chem ^{h:} , and UA ^{i:} | | | | | | | X ^{r:} |
| Coagulation ^{j:} | | | | | | X ^{f:} | X ^{g:} |
| Platelet Count ^{s:} | | | | | | X ^{f:} | X ^{g:} |
| Serum Pregnancy Test (♀ only) | | | | | | | X ^{r:} |
| AE Monitoring | | | | X | | | X |
| ConMeds Monitoring | | | | X | | | |
| Study Drug Administration / PK/PD/Immunogenicity | | | | | | | |
| Blood for free xisomab 3G3 PK | | | | | | | X ^{r:} |
| Blood for free xisomab 3G3 PD (aPTT) ^{s:} | | X ^{o:} | | X ^{o:} | | | |
| Blood for Immunogenicity | | | | | | | X ^{r:} |
| Other Procedures | | | | | | | |
| Blood BUN and Potassium (for Kt/V and URR) | | | | | | X ^{f:} | X ^{g:} |
| Dialysate Analysis | | | | | | X ^{k:} | X ^{k:} |
| Visual Assessment and Processing of Dialyzer Membrane | | | | | | | X ^{l:} |
| Return Visits | | | X | | X | | X |

- a: For details on Procedures, refer to [Section 13](#)
- b: Within 28 days prior to Day -8.
- c: Patients will be admitted to the CRU on Day -8, at the time indicated by the CRU and will remain confined up to Day 6 or prior early termination.
- d: Patients will undergo hemodialysis 3 times a week, on Day -7, Day -5, Day -3, and Day 1, Day 3, Day 5, Day 8, Day 10, and Day 12. For each patient, the hemodialysis will last at least 3 hours as per patient standard schedule which will be the same throughout the study.
- e: Symptom-driven physical examination may be performed at other times, at the PI's or designee's discretion.
- f: To be performed ~ 1 hour prior to the start of hemodialysis.
- g: To be performed at the end of hemodialysis.
- h: Samples for serum chemistry will be obtained following a fast of at least 4 hours, however, in case of dropouts or rechecks, patients may not have fasted for 4 hours prior to the serum chemistry sample is taken.
- i: For anuric patients, urinalysis may not be performed.
- j: Coagulation parameters (activated partial thromboplastin time [aPTT], prothrombin time [PT], and international normalized ratio [INR]).

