8.4.2 Rationale for the Dose Selection

Doses of 0.25 mg/kg and 0.5 mg/kg were selected for this phase 2 study in order to provide adequate PD and PK characterization but still allowing a safety margin should the results differ in this population compared to healthy subjects. The 0.25 mg/kg xisomab 3G3 dose is 2.5-fold higher than the lowest dose in the FIH study. The 0.1 mg/kg dose in the FIH study had a short and modest, yet detectable PD effect (several seconds of temporal aPTT prolongation). The 0.25 mg/kg dose is expected to provide an initial plasma concentration that is within the range of average FXI concentration, the molecular target of xisomab 3G3, in human subjects, and may approach saturation in some individuals after full distribution. Therefore, it has the potential to exert brief pharmacological (anti-inflammatory, antithrombotic) activity, possibly lasting up to a day, until elimination of the antibody and hepatic FXI secretion that neutralizes the antibody.

The 0.5 mg/kg dose was safely administered in the FIH study and allowed adequate characterization of the PK profile in healthy adults. In addition, following a 0.5 mg/kg a prolongation of aPTT was seen, with highest values measured at 24 hours postdose and having a sustained effect for at least 72 hours postdose. The 0.5 mg/kg xisomab 3G3 dose is expected to provide, after complete distribution, a plasma concentration that is approximately twice the average human plasma concentration of the FXI antigen. Therefore, this dose is expected to be overcome by FXI generation later, and have pharmacological activity that lasts longer than the lower dose level.

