## 5. TREATMENT DESCRIPTIONS

Patients will receive a single infusion dose of 0.25 mg/kg xisomab 3G3, 0.5 mg/kg xisomab 3G3, or matching placebo on Day 1 at Hour 0. The dose will be administered proximal to the dialyzer cartridge, into the arterial line immediately after start of HD.

Planned doses for each cohort of the study are as follows:

Cohort 1: 0.25 mg/kg xisomab 3G3 or matching placebo

Cohort 2: 0.5 mg/kg xisomab 3G3 or matching placebo

The patients' weight recorded at check-in will be used to calculate the study drug dose.

Treatments will be described as follows:

Cohort	Treatment	Short Description (used in text)	Long Description (used in Tables Figures and Listings)
Cohorts 1 & 2	P	Placebo (Pooled)	Single IV Infusion of Placebo (Pooled)
Cohort 1	A	0.25 mg/kg xisomab 3G3	Single IV Infusion of 0.25 mg/kg xisomab 3G3
Cohort 2	B	0.5 mg/kg xisomab 3G3	Single IV Infusion of 0.5 mg/kg xisomab 3G3

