**Programmer Note:**

***For Tables 14.2.5.1.4 through 14.2.5.1.6, aPTT baseline will be the average of all pre-dialysis aPTT value on Days -7, -5, -3 and 1, and the change from baseline will be calculated as follows: (post-dialysis/baseline).***

Table 14.2.5.1.7	Individual and Mean Difference Between Pre- and Post-dialysis aPTT Values (unit) – Days -7 to 12 – 0.25 mg/kg Xisomab 3G3 on Day 1 (Safety Population)
Table 14.2.5.1.8	Individual and Mean Difference Between Pre- and Post-dialysis aPTT Values (unit) – Days -7 to 12 – 0.5 mg/kg Xisomab 3G3 on Day 1 (Safety Population)
Table 14.2.5.1.9	Individual and Mean Difference Between Pre- and Post-dialysis aPTT Values (unit) – Days -7 to 12 – Placebo (Pooled) (Safety Population)

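### Within each arm the early aPTT change from baseline mixes drug and dialysis effects, and the SAP neither specifies the placebo contrast that separates them nor keeps the placebo summary statistics

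*SAP*

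**What the plan says.** SAP 7.2.1 fixes the denominator: "the average of pre-dialysis aPTT values on Days -7, -5, -3, and 1 will be calculated as pre-dose baseline". The numerator is any postdose value: "aPTT change from baseline will be calculated by dividing postdose aPTT values from average of pre-dose baseline". Samples are drawn "pre- and post-dialysis on Days -7, -5, -3, 1, 3, 5, and 12", and on the PD schedule at "0.167, 0.5, 1, 2, 3, 4, 6, 8, 12, 16, 24, 48, 96, 120, 144, and 192, hours after xisomab 3G3 start of infusion".

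SAP Section 5 places the dose "into the arterial line immediately after start of HD". Footnote d of the protocol flow chart states that "the hemodialysis will last at least 3 hours as per patient standard schedule". SAP Section 9 puts the session at about 4 hours.

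Two other displays bear on the point:

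- SAP 7.2.1 also forms a post/pre-dialysis fold change session by session on all seven listed days, run-in included. It is shown by arm in Table 11-6 and Tables 14.2.5.1.7 to 14.2.5.1.9.
- Figures 11-6, 14.2.5.2.5 and 14.2.5.2.6 plot the change from baseline for both doses and pooled placebo.

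Two notes do not fit SAP 7.2.1:

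- The programmer note to Tables 14.2.5.1.4 to 14.2.5.1.6 (SAP 10.2) says "the change from baseline will be calculated as follows: (post-dialysis/baseline", where 7.2.1 has postdose values.
- The notes after the Table 14.2.1.1.1 shell (SAP 11.3) say that the placebo aPTT Tables 14.2.5.1.3 and 14.2.5.1.6 carry no summary statistics. SAP 7.2.1 says aPTT is summarized for both doses and pooled placebo.

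**The concern.** The denominator is always taken off dialysis. For the first hours after dosing the numerator is always taken on dialysis or as it ends. Protocol 8.4.1 links perfusion of devices with contact activation, and Protocol 8.5 mentions consumption of blood components by thrombus formation. A shift in aPTT without drug is therefore plausible, although the documents do not quantify one.

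aPTT is a potency marker, and the endpoint is to be read against both pre-treatment and placebo. The pre-treatment half of that reading is the half affected. The lower dose is the more exposed: Protocol 8.4.2 expects activity at 0.25 mg/kg possibly for up to a day, and describes the first-in-human 0.1 mg/kg result as a "short and modest, yet detectable PD effect (several seconds of temporal aPTT prolongation". A dialysis shift of a few seconds could be taken for drug effect or could hide it, and its disappearance after the session could look like offset of effect.

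The placebo arm is the natural remedy, and the plan stops short of using it in numbers.

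**Working it through.** The documents give no aPTT effect size, SD or power figure, so there is no planned figure to reproduce. The sample size was chosen without statistical considerations (Protocol 14.1).

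**1. Samples taken on dialysis.** The postdose times up to 24 h are 0.167, 0.5, 1, 2, 3, 4, 6, 8, 12, 16 and 24 h, which is 11. Those at or before 3 h number 5, and those at or before 4 h number 6. Of all 16 postdose times the counts are 5 and 6. On later dialysis days, flow chart footnote o puts PD samples at least 1 h before the session, so the 48 h and 96 h samples match the baseline state.

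**2. What each ratio estimates.** Let f be the dialysis-only aPTT ratio and g the drug ratio. Both are assumptions.

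- SAP ratio within an arm, during dialysis: f × g
- Placebo on the same baseline and at the same time: f
- Active ÷ placebo: (f × g) ÷ f = g

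With g = 1.30:

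| f (assumed) | SAP ratio, active arm | Placebo | Active ÷ placebo |
|---|---|---|---|
| 0.90 | 1.17 | 0.90 | 1.30 |
| 1.00 | 1.30 | 1.00 | 1.30 |
| 1.10 | 1.43 | 1.10 | 1.30 |
| 1.20 | 1.56 | 1.20 | 1.30 |

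The relative distortion within an arm is f − 1, which is zero if dialysis does not move aPTT. In seconds, on an assumed 35 s baseline, a 5 to 10% shift is 35 × 0.05 = 1.75 s to 35 × 0.10 = 3.5 s.

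**3. What run-in data can correct.** Run-in aPTT is drawn only before and after dialysis. There is no mid-session run-in value, so for the mid-session samples only placebo can separate drug from dialysis. At the end of the Day 1 session, the post/pre fold change is f × g (the pre value is predose) and the run-in fold change is f. Their quotient is g.

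On Days 3, 5 and 12 the pre-dialysis value may already carry drug effect. The same quotient then gives g at the end of the session over g at its start, which is a change across the session and not the total drug effect.

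**4. What the tables would contain.** As the shells stand, Tables 14.2.5.1.3 and 14.2.5.1.6 would list individual placebo values without mean or SD. The coagulation safety summary does not clearly fill the gap: SAP 8.4 refers aPTT to Section 7.2, and the Table 14.3.5.5 shell omits time points already summarized in the PD tables. No active-versus-placebo quantity is defined anywhere for aPTT.

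**5. Precision of a placebo contrast.** Cohorts of 9 to 12 at 2:1 give 6 to 8 active per dose and 3 to 4 placebo per cohort, so 6 to 8 pooled placebo. For the difference between an active and the placebo mean ratio, with assumed SD s, the 95% half-width is 1.96 × s × √(1/n₁ + 1/n₂):

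- s = 0.10, 8 and 8: 1.96 × 0.10 × √(1/8 + 1/8) = 0.098
- s = 0.20, 6 and 6: 1.96 × 0.20 × √(1/6 + 1/6) = 0.226

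These use the normal approximation, so they are slightly too narrow for groups this small.

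**The case against.** A good deal can be said for the plan.

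- **Run-in post-dialysis aPTT is used.** A reader might infer that it is collected and then ignored. It is absent from this one denominator only. The session-by-session fold change shows the drug-free dialysis effect for each arm beside Days 1, 3, 5 and 12.
- **Placebo controls for dialysis.** Placebo patients are randomized within cohort, have the same heparin-free sessions and are plotted on the same measure. A dialysis effect common to the arms cancels in expectation in active versus placebo, and also in one dose against the other. A reader might infer that the dose-dependency comparison is biased; the documents do not support that.
- **A second, post-dialysis baseline would not be better.** It would serve only the end-of-session sample, and changing the denominator within the Day 1 profile could itself create a step at the end of dialysis.
- **The note may be a slip.** The tables are laid out by sampling hour, so the post-dialysis wording probably means postdose.
- **The stakes are limited.** The analysis is descriptive, no decision rule depends on this ratio, and the effect at 0.5 mg/kg in the first-in-human study was highest at 24 h, off dialysis.

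All of this stands, and it rules out a claim that the aPTT analysis is invalid. It does not answer the gap in reporting. The comparison that protects the early reading is left to the eye on a figure, and the placebo numbers behind it are removed from the tables.

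**Conclusion.** The point holds as one of interpretation and reporting. Read within an arm, 5 or 6 of the 11 aPTT ratios in the first 24 h combine drug and dialysis effects. The counts follow from the documents. The size of the mixing does not: the values of f, the 35 s baseline and the SDs are assumptions, and no dialysis effect at all is possible.

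The trial already contains what is needed to separate the two effects. What is missing is a specified placebo contrast and, because of the shell note that conflicts with SAP 7.2.1, the placebo summary statistics. The cancellation assumes that the dialysis effect is common to the arms. If the drug alters that effect, the placebo-relative ratio is the drug effect under dialysis, which is still a meaningful quantity. The matter weighs more for 0.25 mg/kg than for 0.5 mg/kg, where the first-in-human study showed a near-saturating effect.

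**What to change.** In the SAP and its shells:

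1. Keep the single pre-dialysis baseline for the whole profile.
2. Delete the shell note that removes summary statistics from Tables 14.2.5.1.3 and 14.2.5.1.6, so that they agree with 7.2.1.
3. Add to 7.2.1 the change-from-baseline ratio for each dose relative to pooled placebo at each nominal time, preferably with an interval so that its imprecision is visible.
4. Mark the dialysis window on Figure 11-6. Its y-axis shows a ratio, so the label in seconds should go at the same time.
5. For end-of-dialysis samples, compare each patient's post/pre fold change on Days 1, 3, 5 and 12 with that patient's mean run-in fold change (Days -7, -5 and -3). Add a footnote that on Days 3, 5 and 12 the pre-dialysis value may already carry drug effect.
6. Correct the programmer note to Tables 14.2.5.1.4 to 14.2.5.1.6 so that the numerator is the postdose value.

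The cost is SAP and shell wording and a few extra table columns. All samples are already scheduled. The drawback is that the placebo-relative estimates rest on about 6 to 8 placebo patients and will be wide.
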